10.3. Efficacy Analysis

The primary endpoint is mean change from start to end of KZR-616 treatment in TIS.² For the continuous efficacy parameters, within-patient changes will be analyzed as follows:

- (1: primary) by comparing the Baseline and post Baseline observations within patients for the KZR-616 treatment periods combined, ie, W16 versus W0 for patients allocated to the randomized treatment sequence KZR-616 followed by placebo and W32 versus W16 for patients allocated to the randomized treatment sequence placebo followed by KZR-616, combined;
- (2: secondary) by comparing the change from Baseline in Treatment Period 1 between treatments, ie, change from W0 to W16 for patients allocated to the randomized treatment sequence KZR-616 followed by placebo versus change from W0 to W16 for patients allocated to the randomized treatment sequence placebo followed by KZR-616; and
- (3: exploratory) by comparing the last response on test treatment between treatments via a crossover design analysis, ie, W16 for patients allocated to the randomized treatment sequence KZR-616 followed by placebo and W32 for patients allocated to the

randomized treatment sequence placebo followed by KZR-616, combined, versus W16 for patients allocated to the randomized treatment sequence placebo followed by KZR-616 and W32 for patients allocated to the randomized treatment sequence KZR-616 followed by placebo, combined.

The rationale for this priority order is as follows. The usual crossover analysis for this design is prespecified as exploratory since it is unknown whether that analysis would be confounded by carryover effect. In order to maximize the precision for assessment of KZR-616 effect, it is assessed primarily via all patients' Baseline versus post-Baseline KZR-616 assessment and secondarily by the Treatment Period 1 between-treatment comparison. Summary statistics, including 95% confidence intervals, will be provided for each treatment for each of the 3 types of analysis. Within-patient changes will be analyzed via paired t-tests and corroborated by signed rank tests. Between-patient differences will be analyzed via analysis of covariance, with Baseline as a covariate. The crossover analysis will be via a mixed-model repeated-measures analysis. Normality will be assessed graphically and via the Shapiro-Wilk statistic. If substantial departure from normality is observed, transformations, eg, natural log and rank, will be explored. P values will be 2-sided with at the type 1 error level 0.05.

Binary endpoints will be summarized by counts and percent and 95% confidence intervals via Clopper-Pearson method. Additional analyses will be specified in the SAP.

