3.1.3. Study Design Rationale

This placebo-controlled double-blind crossover study is designed to minimize bias in the evaluation of KZR-616 in patients with DM/PM and to maximize the opportunity for each patient to contribute data. All patients may still receive background treatment in the form of the allowed concomitant therapies as described in the study exclusion criteria ([Section 4.3](#)). A crossover design was selected for use in this study to:

- Increase the power of the study because not only will there be the opportunity for evaluation of between-group comparisons, but the patients initially treated with placebo can serve as their own controls
- Data for bortezomib allude to maintenance of effect of proteasome inhibition postdosing.³ The Treatment and SFU Periods allow for evaluation of the treated population after drug discontinuation in terms of both safety and efficacy; these data are best obtained from those patients that start on KZR-616 first and then cross over to placebo.

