3.2. Minimization of Bias

3.2.1. Randomization

Patients will be allocated to a randomized treatment sequence (Arm A: KZR-616 followed by placebo; Arm B: placebo followed by KZR-616) in a 1:1 fashion. Patients will receive the first assigned study drug treatment in Treatment Period 1 (W0 through before dosing at W16)

and cross over to receive the next study drug treatment beginning on the first day of Treatment Period 2 (administration of the first dose at W16 through W32). Patients will be stratified according to their diagnosis of PM or DM. Patients will be stratified by their diagnosis of DM or PM.

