7.2.4.1. Total Improvement Score

The Myositis Response Criteria are recommended for use as primary endpoints in myositis therapeutic trials. The criteria use the 6 IMACS core set measures, combining the absolute percentage change in each with varying weights to obtain a TIS on a scale of 0-100. Different thresholds of improvement have been set for minimal, moderate, and major response. The TIS may be used as a continuous outcome measure or as a categorical outcome of improvement (minimal, moderate, or major improvement). The TIS can be calculated using the 2016 ACR/EULAR criteria² using the web calculator located at:
https://www.niehs.nih.gov/research/resources/imacs/response_criteria/adult.html

The User's Guide is located at:

https://www.niehs.nih.gov/research/resources/imacs/response_criteria/users_guide_for_the_adult.html

[dult_dermatomyositis_and_polymyositis_response_criteria_online_calculator_508.pdf](https://www.niehs.nih.gov/research/resources/assets/docs/duilt_dermatomyositis_and_polymyositis_response_criteria_online_calculator_508.pdf)
(Last accessed: 28 February 2019)

Investigators will not be required to make these calculations for the study.

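### The primary test compares TIS change on KZR-616 with zero, so a significant result does not by itself show a drug effect

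*Combined protocol and SAP*

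**What the plan says.** Section 10.3 lists three analyses of continuous efficacy endpoints. The first, labelled primary, is made "by comparing the Baseline and post Baseline observations within patients for the KZR-616 treatment periods combined". Arm A contributes W16 versus W0 and Arm B contributes W32 versus W16. The test is given as "Within-patient changes will be analyzed via paired t-tests and corroborated by signed rank tests", two-sided at 0.05. The second is the randomised comparison of change from W0 to W16 between arms: "Between-patient differences will be analyzed via analysis of covariance, with Baseline as a covariate". The third, exploratory, is the crossover analysis.

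The reason for the order is that carryover might confound the crossover analysis, and then: "In order to maximize the precision for assessment of KZR-616 effect, it is assessed primarily via" the start-to-end change on KZR-616, and only secondarily by the Period 1 comparison. The note closing section 2.2.1 and the synopsis say the same. Section 10.3 also promises "Summary statistics, including 95% confidence intervals, will be provided for each treatment for each of the 3 types of analysis".

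Section 7.2.4.1 describes the Total Improvement Score (TIS) as "combining the absolute percentage change in each with varying weights to obtain a TIS on a scale of 0-100". Section 3.1 defines Baseline as Day 1 of W0. Section 10.1 gives 24 patients 80% power for improvement from Baseline at an effect size of 0.6, 90% at 0.7, and a minimum significant observed effect of 0.42. It states that no prior summary statistics on TIS change are available.

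**The concern.** A paired test against zero asks whether patients changed while on KZR-616. It does not ask whether they changed because of KZR-616. The plan nevertheless names this test as the main assessment of the drug's effect, in a trial that has a randomised, blinded placebo arm.

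The carryover argument explains why the crossover analysis is exploratory. It does not explain why the Period 1 comparison, which carryover cannot touch, ranks below an uncontrolled one. What remains is precision, and that gain comes from pooling all 24 patients and leaving out the placebo contrast.

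At stake is the reading of the headline result. The plan allows a significant primary analysis beside a Week 16 difference near zero, and does not say what would then be concluded. The only power figures in section 10.1 belong to the uncontrolled test.

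**Working it through.** **Inputs.** From the protocol: n = 24, about 12 per arm, two-sided alpha 0.05, effect sizes in SD units (synopsis, sections 4.1, 10.1 and 10.3). Assumed: the size of non-drug change over a KZR-616 period, because the documents give none.

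**1. Reproduce section 10.1.** One-sample t-test, 23 df, critical value 2.069, noncentrality d × √24.
- d = 0.6: 0.6 × 4.899 = 2.939, power 80.4%.
- d = 0.7: 0.7 × 4.899 = 3.429, power 90.7%.
- Minimum significant observed effect: 2.069 / 4.899 = 0.422.

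All three stated figures reproduce. They are correct for a test of change against zero.

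**2. Inert drug.** Use the same formula, with d replaced by a non-drug change m in both arms' KZR-616 periods.

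| m (SD, assumed) | Noncentrality | t-test significant |
|---|---|---|
| 0 | 0 | 5.0% |
| 0.1 | 0.490 | 7.6% |
| 0.2 | 0.980 | 15.6% |
| 0.3 | 1.470 | 29.1% |
| 0.5 | 2.449 | 65.0% |
| 0.6 | 2.939 | 80.4% |

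Requiring the signed rank test to be significant as well gives about 6%, 26% and 61% at 0.1, 0.3 and 0.5 (simulation, 100,000 trials). The corroborating test therefore changes little in this model. A wholly non-drug change of 0.6 SD succeeds as often as the drug effect for which the trial was sized.

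**3. Arm B's later start.** Arm B starts from W16, so gain during its placebo period is already in the starting value. If Arm B has no further non-drug change and Arm A changes by m, the pooled mean is (12 × m + 12 × 0) / 24 = m/2. For m = 0.1, 0.3 and 0.5 that is 0.05, 0.15 and 0.25 SD. By the table the rates lie between 5.0% and 7.6%, between 7.6% and 15.6%, and between 15.6% and 29.1% (simulated: about 6%, 11% and 20%). The rate is lower but still not controlled.

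**4. The TIS floor.** A 0 to 100 score built from improvement in core measures appears to be zero at its own reference visit and unable to go below zero. This is inferred from sections 2.2.1 and 7.2.4.1; it is not stated. If so, Arm A's mean change is zero only if no patient scores. The same holds in Arm B if TIS is re-zeroed at W16. If Arm B's change is instead a difference of two W0-referenced scores, it can be negative. Section 10.3 does not say which applies.

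To illustrate the re-zeroed case, let k of 24 patients score 20 and the rest 0, so t = √(23k / (24 − k)).
- k = 4: t = √(92/20) = 2.145, p = 0.043; exact signed rank p = 2/2⁴ = 0.125.
- k = 6: t = √(138/18) = 2.769, p = 0.011; signed rank p = 2/2⁶ = 0.031.

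The all-or-nothing score is an assumption, and the plan's normality checks would flag the k = 4 data.

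**5. The randomised comparison.** With the same non-drug change in both arms during Period 1, a 12 versus 12 t-test was significant in 5.0% of simulated trials at 0.3 SD and 5.2% at 0.6 SD.

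**6. Its precision and power.** Standard errors are 1/√24 = 0.204 SD for analysis (1) and √(2/12) = 0.408 SD between arms. With 22 df the 95% CI half-width is 2.074 × 0.408 = 0.85 SD. Power for a drug-minus-placebo difference, before covariate adjustment, is 29% at 0.6 SD, 37% at 0.7 SD and 80% at about 1.2 SD.

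**The case against.** The strongest reply is that this is an openly declared choice in a small initial trial. The order and its reason are stated, the Week 16 comparison is prespecified, and confidence intervals are promised for each treatment. That stands. A reader might infer that the trial lacks a placebo comparison or that its power figures are wrong; the documents support neither.

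A reader might also infer that all non-drug improvement is credited to the drug. That goes too far, as step 3 shows for Arm B. For the same reason the remark in section 3.1.3 that "the patients initially treated with placebo can serve as their own controls" is not clearly contradicted: comparing W32 with the same patient's end-of-placebo value is one way to honour it.

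Nor is the error rate shown to be inflated by a known amount. Entry requires prior inadequate response or intolerance (section 4.2), background therapy is to stay stable (section 6.2.1.1), and no new exercise regimen may start (section 6.2.2.1). These limit non-drug change but do not exclude it. The rule that rescued patients count as nonresponders (section 6.2.2) is not tied to mean TIS change, so it gives little reassurance here. Spreading scores over a range instead of using all-or-nothing values lowers the re-zeroed responder rates.

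Finally, section 10.1 already says its power is for improvement from Baseline. True, but section 10.3 then describes the same test as assessing the KZR-616 effect.

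**Conclusion.** The concern holds. Analysis (1) cannot separate a drug effect from other change during the KZR-616 period, and its false-positive rate for a drug effect is not controlled at 5%. This follows from the missing placebo term and needs no assumption.

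The size does need one. For an assumed 0.1, 0.3 or 0.5 SD of non-drug change in both arms' KZR-616 periods, the t-test rate is 8%, 29% or 65%, and lower if Arm B has none after W16. The floor argument depends on TIS being zero at its reference visit, which the documents imply but do not state.

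The defect lies in what a significant primary result is said to show. It touches the primary endpoint and the only stated power, so it should be corrected before unblinding.

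**What to change.** The ranking of the three analyses can stay.

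1. In sections 2.2.1 and 10.3 and the matching synopsis text, describe analysis (1) as an uncontrolled within-patient estimate with its 95% CI. Add, for example: *Analysis (1) includes any improvement during the KZR-616 period that is not due to the drug; significance against zero does not by itself show a KZR-616 effect.*
2. Base any conclusion that KZR-616 differs from placebo on the planned Week 16 between-arm comparison. For TIS, the Baseline covariate is a constant if TIS is zero at W0. Replace it with the randomisation stratum (section 3.2.1: "Patients will be stratified according to their diagnosis of PM or DM") and a collected baseline core measure such as MMT-8.
3. Use one TIS construction in both arms and state Arm B's reference visit.
4. In section 10.1, state that 80% and 90% apply only to change from zero. Add the 12 versus 12 power for a drug-minus-placebo difference: 29% at 0.6 SD, 37% at 0.7 SD and 80% at about 1.2 SD. Note that these effect sizes equal the change-from-Baseline ones only if placebo change is zero.

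**Cost.** Text edits, carried into the SAP that section 10 says will be prepared; no new patients, visits or data. The downside is that the placebo-controlled conclusion has low stated power. It would rest mainly on the estimate and its CI, with a half-width of about 0.85 SD before covariate adjustment.

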2.2. Study Endpoints

2.2.1. Efficacy Endpoints

The primary efficacy endpoint is:

- Mean change from start to end of KZR-616 treatment in the Total Improvement Score (TIS), which ranges from 0 to 100.

Secondary efficacy endpoints are:

- Proportion of patients with an increase ≥ 20 points on the TIS from start to end of KZR-616 treatment. The categories and ranges of scores for improvement are: 20-39 points being minimal improvement, 40-59 points being moderate improvement, and ≥ 60 points being major improvement
- Proportion of patients from start to end of KZR-616 treatment meeting International Myositis Assessment and Clinical Studies Group (IMACS) Definition of Improvement (DOI). The IMACS DOI is $\geq 20\%$ improvement in at least 3 of 6 core set activity measures, with no more than 2 core set activity measures (CSAMs) worsening by $\geq 25\%$ (the Manual Muscle Testing-8 Muscle Groups [MMT-8] cannot be a worsening measure)
- Absolute change and percent change from start to end of KZR-616 treatment in the IMACS individual CSAMs
- For patients with DM, the mean change from start to end of KZR-616 treatment in the Cutaneous Dermatomyositis Disease Area and Severity Index (CDASI)
- For patients with DM, the mean change from start to end of KZR-616 treatment in the Peak Pruritus Numeric Rating Scale (NRS).

Exploratory efficacy endpoints are:

- Mean change over time from start to end of KZR-616 treatment in the TIS in all patients, patients with DM only, and in patients with PM only
- Proportion of patients over time with an increase of ≥ 20 , ≥ 40 , or ≥ 60 points on the TIS from start to end of KZR-616 treatment in all patients, in patients with DM only, and in patients with PM only
- For patients with an increase of ≥ 20 points on the TIS from Baseline to W16, the proportion of patients with no change or increase in their TIS at W32 for all patients, in patients with DM only, and in patients with PM only
- Mean change and mean percent change over time from start to end of KZR-616 treatment in the IMACS individual CSAMs and core set damage measures (CSDMs) for all patients, in patients with DM only, and in patients with PM only
- Mean change from Baseline over time from start to end of KZR-616 treatment in the FI-2, the FI-3 and the individual components of the FI-3 for all patients, in patients with DM only, and in patients with PM only
- For patients with DM, mean change over time from start to end of KZR-616 treatment in the CDASI

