3. STUDY DESIGN

3.1. Type and Design of Study

This is a Phase 2 randomized, double-blind, placebo-controlled, crossover, multicenter study designed to evaluate the safety, tolerability, efficacy, PK, and PD of treatment with KZR-616 in patients with active PM or DM.

Patients will be evaluated for eligibility during the Screening Period. Eligible patients will be allocated in a 1:1 fashion to a randomized treatment arm (Arm A or Arm B). Patients will be stratified by their diagnosis of PM or DM.

During the 32-week treatment period, patients will receive study drug SC once weekly. The 16 weeks of dosing during Treatment Period 1 begins at Week (W) 0 and continues through W15 (ie, ends immediately before dosing at Week 16 [approximately Day 113]); patients allocated to Arm A will receive KZR-616 and those in Arm B will receive placebo. The 16 weeks of dosing during Treatment Period 2 begins with administration of the first dose at W16 and continues through W31 (ie, ends immediately before Week 32); patients allocated to Arm A will receive placebo and those in Arm B will receive KZR-616.

This study will be conducted on an outpatient basis. Study visits will occur at Screening, W0, W4, W8, W12, W16, W20, W24, W28, W32, W36, and W40. Day 1 of W0 will be defined as Baseline. The W36 and W40 visits will comprise the Safety Follow-up (SFU).

Randomized patients who withdraw from the study prior to W32 will be requested to undergo the Early Termination Visit (ETV) procedures, and all patients who withdraw prematurely also will be requested to return for a SFU visit 9 weeks (W40 visit procedures) after receipt of their last dose of the study drug.

Efficacy assessments will be performed for all patients, unless indicated otherwise, and will include:

- IMACS core set Activity and Damage measures
 - MMT-8
 - Physician Global Assessment (MDGA)
 - Patient Global Assessments of Disease Activity (PtGADA)
 - Health Assessment Questionnaire-Disability Index (HAQ-DI)
 - Muscle enzymes (clinical laboratory assessments): CK, aldolase, LDH, alanine aminotransferase (ALT), and aspartate aminotransferase (AST)
 - Myositis Disease Activity Assessment Tool (MDAAT, 2005 version)
 - Myositis Damage Index (MDI)
 - Patient Global Assessment of Disease Damage (PtGADD).
- Functional Index-2 (FI-2, performed for the dominant side only).
- Functional Index-3 (FI-3) assessments:
 - 30-second chair stand test

- Timed up and go test
- 6-minute walk distance.
- MDGIC

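### The reference visit for Arm B's Week 32 TIS is not stated; if it is Week 0, the pooled primary mean and the 20-point responder rule mix two different quantities

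*Combined protocol and SAP*

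**What the plan says.** Section 10.3 states: "The primary endpoint is mean change from start to end of KZR-616 treatment in TIS". Analysis (1), the primary one, proceeds "by comparing the Baseline and post Baseline observations within patients for the KZR-616 treatment periods combined". For Arm A this is "W16 versus W0 for patients allocated to the randomized treatment sequence KZR-616 followed by placebo", and for Arm B it is "W32 versus W16 for patients allocated to the randomized treatment sequence placebo followed by KZR-616, combined". The pooled values go into a paired t-test, corroborated by a signed rank test, at two-sided 0.05.

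Section 7.2.4.1 describes the TIS as "combining the absolute percentage change in each with varying weights to obtain a TIS on a scale of 0-100". Each value therefore needs a reference visit, and no value can be below 0. Section 3.1 gives the only general definition: "Day 1 of W0 will be defined as Baseline".

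Section 2.2.1 sets the first secondary endpoint as the proportion of patients whose TIS rises by 20 points or more over the KZR-616 period. It also has an exploratory durability endpoint: among patients who gained at least 20 points from Baseline to Week 16, "the proportion of patients with no change or increase in their TIS at W32".

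No section states the visit from which Arm B's Week 32 TIS is calculated. Section 7.2.4.1 points to a web calculator. Section 10 defers detail to an SAP, and the supplied text has no SAP section that settles the matter.

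**The concern.** The primary endpoint is a change in a score that is already a change. For Arm A this does no harm: nothing has changed at Week 0, so the Week 0 score is 0 and the change is simply the Week 16 score. For Arm B the result depends on the unstated reference visit.

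On a Week 0 reference, Arm B's value is one improvement score minus another. A patient who worsens on KZR-616 can pull Arm B's contribution below 0, but no patient can do that in Arm A. A patient who scored 40 on placebo can gain at most 60 on drug. The same drug effect is thus measured differently according to sequence and placebo-period response.

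The responder rule is affected too. The 20, 40 and 60 cut-offs are categories of the TIS itself. An Arm B patient going from 45 at Week 16 to 60 at Week 32 has reached the major-improvement category from Week 0, yet the increase of 15 fails the 20-point rule.

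If the choice stays open, the two readings give different means, ranges and responder counts, and the choice could be made after the data are seen.

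**Working it through.** **The plan's own figures (section 10.1).** Inputs: 24 patients, two-sided alpha 0.05, standardized effects 0.6 and 0.7. A one-sample t-test with 23 df (noncentral t) gives power of 80.4% and 90.7%, against the stated 80% and 90%. The smallest significant observed effect is t(0.975, 23)/√24 = 0.422, against the stated 0.42. These figures reproduce. They rest on a standardized effect only, so they do not depend on the reference visit.

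**Ranges under each reading.**

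| | Arm A | Arm B |
|---|---|---|
| Week 0 reference | TIS(W16), 0 to 100 | TIS(W32) − TIS(W16), from −TIS(W16) to 100 − TIS(W16) |
| Start-of-period reference | TIS(W16 from W0), 0 to 100 | TIS(W32 from W16), 0 to 100 |

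**Size, by illustration.** The documents give no TIS mean or SD, so everything below is assumed. Model: a latent level at each visit with independent noise of SD s; score = latent change floored at 0. A change between two visits has SD S = s√2, and its floored mean is m·Φ(m/S) + S·φ(m/S).

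- *No drug or placebo effect, s = 12.* S = 17.0. Arm A: 17.0 × 0.399 = 6.8. Arm B on the Week 0 reading: 6.8 − 6.8 = 0, with one third of values negative. Gap about 7 points. Re-based to Week 16, Arm B is also 6.8.
- *Placebo change 15, drug change 30, s = 15.* S = 21.2. Arm A: 30.7. Arm B on the Week 0 reading: 45.1 − 18.0 = 27.1, with about 8% of values negative. Gap 3.6, about 4 points. Re-based, Arm B is 30.7. The pooled mean is 28.9 against 30.7.
- *Alternative null: independent period changes of SD 20.* Arm A 7.9, Arm B 3.3 on the Week 0 reading and 8.0 re-based. Gap 4.6.

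**What the test against 0 does with no drug effect (12 + 12 patients, paired t-test).**

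- s = 12 null: pooled mean 3.4 and about 30% of trials significant on the Week 0 reading; pooled mean 6.8 and about 99% significant after re-basing.
- Wider range: latent improvement from Week 0 with mean 0 to 20 and SD 15 to 25 at both visits, correlation 0.5 to 0.8. About 30% to 96% significant on the Week 0 reading, 99% to 100% re-based. Arm A's mean runs from about 6 to 23. Arm B's is about 0 on the Week 0 reading and about 4 to 10 re-based.

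In that wider range, part of the arm gap is non-drug improvement that occurs in Period 1 and then stops. Re-basing does not remove that part. It gives the two arms one definition and one range, not necessarily equal means.

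**The case against.** The strongest reply is that the protocol already intends a Week 16 reference in Arm B. The endpoint runs from the start to the end of KZR-616 treatment, and Arm B's start is Week 16. Section 10.3 treats Week 16 as the Baseline observation of Arm B's drug period. Since the TIS is built from changes, Week 32 versus Week 16 can be read simply as the TIS between those visits. On that reading both arms share one definition.

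This stands as a permitted reading. A reader might infer that the plan fixes Week 0 as Arm B's reference, so that the mixing is certain; the documents do not support that, because no section says so. Nor do they settle on Week 16. The single Baseline definition points to Week 0. The durability endpoint needs a Week 32 score comparable with the Baseline-to-Week 16 score, and the exploratory crossover analysis sets Week 16 and Week 32 responses side by side. The word Baseline currently serves for both visits.

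A second reply is that re-basing makes the primary test worse. That is correct, as the null rejection rates show: worsening would then count in neither arm. It does not excuse leaving the reference undefined, but it limits what the change achieves.

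Third, the drug-effect illustration shifts the pooled mean by only 1.8 points (30.7 − 28.9), from one floored latent variable rather than six weighted measures. That is fair. The case rests on the missing definition more than on the size. The secondary Period 1 comparison uses Week 0 in both arms and is unaffected.

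**Conclusion.** The concern holds conditionally. The reference visit for Arm B's Week 32 TIS is not stated, so the primary endpoint is not uniquely defined. If the only defined Baseline is used, the pooled mean averages a score confined to 0 to 100 with a difference of scores that can be negative, and the 20-point rule means different things in the two arms.

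Under the assumed visit-noise model the arm gap is about 7 points with no drug effect (SD 12) and about 4 points with a drug change of 30 (placebo change 15, SD 15). These are illustrations, not estimates for this trial.

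A reader might also infer that a common reference visit would make the primary test valid. It would not: a score that cannot fall below 0 is then tested against 0, and the assumed null gives about 99% rejections against about 30% on the Week 0 reading. The sample-size arithmetic is not in error.

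**What to change.** In sections 7.2.4.1 and 10.3, before unblinding:

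1. State that the TIS for each treatment period is calculated from the core set values at the start of that period: Week 0 for Period 1, Week 16 for Period 2.
2. Apply the 20-, 40- and 60-point thresholds directly to that score.
3. Keep the Week 0-referenced Week 32 TIS only for the durability endpoint, and label it as such.
4. Report the pooled KZR-616 mean with its confidence interval as descriptive, without a paired t-test or signed rank test against 0. Every non-zero re-based score is positive, so both tests reject almost always.
5. Rest any efficacy conclusion on the already planned Period 1 comparison with placebo. The Baseline covariate in its ANCOVA needs restating for this endpoint, since the TIS at Week 0 is 0 for everyone.

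The derivation costs only wording: the core set measures are already scheduled at Week 16 (Table 4), and no visit is added. The real cost is inferential. With 12 patients per arm, a between-arm standardized effect of 0.6 has about 31% power and 0.7 about 40% (normal approximation), so the Period 1 comparison will be imprecise and should be presented that way.

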10.1. Sample Size Calculation

Prior summary statistics on change from Baseline in TIS score are not available. Hence, statistical power is quantified via standardized effect size (mean difference divided by pooled standard deviation [SD]). A sample size of 24 patients has 80% power to yield a statistically significant ($\alpha=0.05$ 2-sided) improvement from Baseline if the true underlying effect size is 0.6 (90% power if true effect size is 0.7). The minimum observed effect size that would yield statistical significance is 0.42. This level of statistical precision is thought to be adequate for this initial trial of KZR-616 in PM and DM.

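### The primary paired t-test combines two randomised sequences without a sequence term, so its interval is wider than necessary if the sequence means differ; a cheap gain in precision, not an error

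*Combined protocol and SAP*

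**What the plan says.** Section 10.3 sets the primary comparison as W16 against W0 for Arm A (KZR-616 first), joined with "W32 versus W16 for patients allocated to the randomized treatment sequence placebo followed by KZR-616, combined". The test is given in one sentence: "Within-patient changes will be analyzed via paired t-tests and corroborated by signed rank tests". No factor for sequence or period is named for this analysis. Analysis of covariance is named for the Period 1 between-arm comparison, and a mixed model for the exploratory crossover analysis. The error level is given as "P values will be 2-sided with at the type 1 error level 0.05". Section 10.3 justifies the order of the analyses by the wish for maximum precision on the KZR-616 effect.

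Section 10.1 sizes the trial on a "standardized effect size (mean difference divided by pooled standard deviation [SD"]). It says: "A sample size of 24 patients has 80% power to yield a statistically significant" result at a true effect size of 0.6, and gives 90% at 0.7. It adds: "The minimum observed effect size that would yield statistical significance is 0.42". It does not say over which groups the SD is pooled. The synopsis plans about 12 patients per arm.

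Section 10 refers to a detailed SAP for further analyses. No sequence-adjusted version of the primary analysis appears in the text available.

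**The concern.** The arms are fixed groups set by 1:1 randomisation. Arm A contributes changes from study entry, and Arm B contributes changes that begin after 16 weeks of placebo. Their mean changes can differ for several reasons:

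- a period effect;
- a placebo response already banked by W16;
- the scoring of the endpoint. Section 7.2.4.1 describes the TIS as a 0 to 100 score built from change in six core measures, and Section 3.1 sets Baseline at W0. If the TIS is scored from W0, Arm A starts at zero while Arm B may start above it and can fall. The documents do not say whether the score is reset at W16.

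A difference between two groups of fixed size is not sampling error of the combined mean, but a one-sample SD counts it as if it were. With 24 patients and no replacement of withdrawals (Section 8.2), the precision given up matters, and precision is the stated reason for putting this analysis first.

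**Working it through.** **Inputs from the documents.** N = 24, about 12 per arm; two-sided alpha 0.05; effect sizes 0.6 and 0.7; smallest significant observed effect 0.42. **Assumed:** D, the true difference between the two sequence mean changes in units of the within-sequence SD, shown from 0 to 1.5. The documents give no value.

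**Step 1: reproduce Section 10.1.** One-sample t-test, 23 df, noncentrality = ES × √24.

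- ES 0.6: power 80.4%. ES 0.7: power 90.7%.
- Smallest significant observed effect: t(0.975, 23)/√24 = 2.069/4.899 = 0.422.

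All three agree with the plan, so its figures are those of the planned test.

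**Step 2: what D does to the SD.** With 12 + 12 patients and within-sequence variance 1, the expected variance of the combined changes is 1 + (24/23) × D²/4.

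- D = 0.5: √(1 + 0.0652) = 1.032.
- D = 1.0: √(1 + 0.2609) = 1.123.

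**Step 3: power and interval, average effect 0.6 within-sequence SD.** For the planned test the mean is normal with variance 1/24, and 23s² is noncentral chi-square with 23 df and noncentrality 24D²/4. The sequence-adjusted test uses the within-sequence SD on 22 df. Results are by numerical integration; simulation with 200,000 trials per case agrees to within about 0.2 points of power.

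| D | Planned test, power | With sequence term, power | Planned 95% interval, coverage | Planned width / adjusted width |
|---|---|---|---|---|
| 0 | 80.4% | 80.2% | 95.0% | 0.998 |
| 0.5 | 78.5% | 80.2% | 95.6% | 1.030 |
| 1.0 | 72.8% | 80.2% | 97.1% | 1.121 |
| 1.5 | 63.2% | 80.2% | 98.5% | 1.259 |

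**Step 4: the other reading of the pooled SD.** Suppose the 0.6 is measured on the SD of all 24 changes combined. The true mean is then 0.6 × the factor in Step 2. Planned power at D = 0.5, 1.0 and 1.5 is about 81%, 83% and 85%. With a sequence term it is about 83%, 88% and 94%. The planned test meets its stated power on this reading, but is still the less efficient of the two.

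**Step 5: cost of the sequence term if D = 0.** The critical values are 2.074 (22 df) and 2.069 (23 df); the ratio is 1.0025. The interval is 0.2 to 0.3% wider.

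**Step 6: uneven completers, assumed 12 against 8.**

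- Shift of the combined mean from the equally weighted mean: D × (12 − 8)/(2 × 20) = 0.10 SD at D = 1.0.
- Standard error of the equally weighted mean: √[(1/12 + 1/8)/4] = 0.228, against √(1/20) = 0.224 for the combined mean, so about 2% wider.
- If D = 0, simulated power is 70.1% with the sequence term and 72.1% without.

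**The case against.** A reader might infer that the power stated in Section 10.1 is not delivered. The documents do not support that. Power is stated on a standardised scale, and its figures are those of the planned one-sample test. If the undefined pooled SD is the SD that this test uses, any sequence difference is already in the denominator and power never falls below 80%. The 0.42 threshold also holds on that SD whatever D is. Only on the within-sequence reading is there a shortfall, and it is about 2 points or less up to D = 0.5.

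A reader might also infer that the 95% interval fails. The direction is the opposite: with equal arms it covers at least 95%, and the type 1 error is not inflated.

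The large losses need large differences. With an average effect of 0.6 SD, D = 1.0 means sequence effects of 0.1 and 1.1 SD, and D = 1.5 means −0.15 and 1.35 SD. At that point one may fairly ask whether the two should be averaged at all. This stands, and it is why each sequence's mean should be reported beside the combined estimate.

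The plan's wording also fits a patient-weighted mean, so equal weighting of the sequences is a choice and not a correction of a stated estimand. The 0.10 SD shift needs both 12 against 8 completers and D = 1.0, and neither figure is in the documents. A by-sequence analysis may also be in the SAP, which is not in the text available.

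These arguments reduce the claim. They do not show the planned test to be as efficient: on either reading of the SD the sequence term gains about 1.6 points of power at D = 0.5 and about 5 to 7 at D = 1.0, for at most 0.2 points lost at D = 0 with equal arms.

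**Conclusion.** The planned primary test is sound and, with equal arms, conservative; the figures in Section 10.1 are correct for it. It is less precise than it need be if the sequence mean changes differ: an interval about 3% wider at D = 0.5 and 12% wider at D = 1.0. The power figures of 78.5% and 72.8% apply only to an effect of 0.6 on the within-sequence SD. All of this rests on an assumed D, equal within-sequence variances, approximate normality and 12 patients per arm. At D = 0.25 the planned test still has about 80% power, so a small difference would cost almost nothing. This is a cheap improvement that serves the plan's own aim, not an error in stated power or coverage.

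**What to change.** In Section 10.3 and the SAP, analyse the within-patient change in a linear model with sequence (Arm A or Arm B) as an effect-coded factor. Test and estimate the intercept, which is the equally weighted mean of the two sequence means, using the within-sequence residual SD (22 df at N = 24). Report each sequence's mean change with its 95% interval. Keep the paired t-test and signed rank test as sensitivity analyses.

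In Section 10.1, state that the pooled SD is the within-sequence SD of the changes. On 22 df the figures become 80.2%, 90.6% and 2.074/√24 = 0.423, so the printed 80%, 90% and 0.42 can stay.

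The cost is some wording and one degree of freedom: 0.2 to 0.3% on the interval if the sequences do not differ. If completers are uneven and the sequences do not differ, the equally weighted mean is slightly less precise, about 2% wider at 12 against 8. No change to the conduct of the trial or to data collection is needed.
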